11.3.4 Changes in Cholesterol Levels

- Change at each of the selected scheduled testing timepoints (Weeks 12-28, every 8 weeks onward until Week 52) from baseline in:
 - Total cholesterol,
 - Low-density lipoprotein/high-density lipoprotein ratio,
 - Non-HDL cholesterol.

The mean change in these 3 parameters at each post-dosing time point from baseline will be analyzed and compared between the 2 treatment groups using MMRM model adjusting baseline value as covariate, treatment group, visit, the interaction of treatment and visit, and stratification factors as fixed effects. The same strategy as that used in MMRM for Hb will be used to choose variance covariance structure.

- Proportion of subjects achieving LDL target of <100 mg/dL averaged over Weeks 12-28 of treatment for Subjects with Baseline LDL \geq 100 mg/dL. The proportion of subjects achieving LDL target will be compared between the 2 treatment groups using logistic regression model adjusting for baseline LDL as covariate and treatment group and stratification factors as fixed effects.

11.3.5 Blood Pressure Effect

- Proportion of subjects achieving blood pressure treatment goal in ESRD subjects (pre dialysis systolic BP <140 mmHg systolic and diastolic BP <90 mmHg) averaged over Weeks 12-28. The proportion of subjects achieving blood pressure goal will be compared between the 2 treatment groups using logistic regression model adjusting for baseline pre dialysis systolic and diastolic BP as covariates and treatment group and stratification factors as fixed effects.
- Time to a treatment-emergent AE (TEAE) of hypertension. Time to a TEAE of hypertension will be analyzed using the Cox Proportional Hazards model adjusting for treatment group and stratification factors as fixed effects.
- Time to exacerbation from baseline of antihypertensive therapy. Time to intensification from baseline of antihypertensive therapy will be analyzed using the Cox Proportional Hazards model adjusting for treatment group and stratification factors.

Subject with exacerbation of hypertension is defined as meeting at least 1 of the following criteria:

- An increase from baseline of ≥ 20 mmHg predialysis systolic BP (sBP) and predialysis SBP >170 mmHg, or
- An Increase from baseline of ≥ 15 mmHg predialysis diastolic BP (dBP) and predialysis DBP >100 mmHg
- Proportion of subjects with a treatment-emergent AE of hypertension. The proportion of subjects with a TEAE of hypertension will be compared between the 2 treatment groups using logistic regression model adjusting for baseline predialysis systolic and diastolic BP as covariates and treatment group and stratification factors as fixed effects.
- Proportion of subjects with exacerbation from baseline of antihypertensive therapy. The proportion of subjects with exacerbation from baseline of antihypertensive therapy will be compared between the 2 treatment groups using logistic regression model adjusting for baseline predialysis systolic and diastolic BP as covariates and treatment group and stratification factors as fixed effects.

11.3.6 Vascular Access Thrombosis (HD subjects):

- Time to a TEAE of vascular access thrombosis will be analyzed using the Cox Proportional Hazards model adjusting for treatment group and stratification factors.
- Proportion of subjects with a TEAE of vascular access thrombosis will be analyzed using CMH model adjusting for treatment group and stratification factors.

11.3.7 Health Related Quality of Life (HRQoL) and EQ-5D-5L Benefits of Anemia Therapy

The Medical Outcomes Study 36-Item Short-Form Health Survey (SF-36) is a multi-purpose, short-form health survey with 36 questions (Appendix 3). It yields an 8-scale profile of functional health and well-being scores as well as psychometrically-based physical and mental health summary measures. It is a generic measure, as opposed to one that targets a specific age, disease, or treatment group. Accordingly, the SF-36 has proven useful in surveys of general and specific populations, comparing the relative burden of diseases, and in differentiating the health benefits produced by a wide range of different treatments.

The SF-36 contains 36 items that measure eight dimensions: (1) physical functioning (PF); (2) role limitations due to physical health problems (RP); (3) bodily pain (BP); (4) social functioning (SF); (5) general health perceptions (GH); (6) role limitations due to emotional problems (RE); (7) vitality, energy or fatigue (VT); and (8) mental health (MH).

Item scores for each dimension are coded, summed, and transformed to a scale from 0 to 100, with higher scores indicating better self-perceived health (Table 7). The transformed items are then averaged to give the subscales. The subscales are averaged to give the composite scores. The composite scores are averaged to give the overall score. The reliability and validity of the SF-36 is well documented in a variety of different subject groups, including subjects with vascular diseases.

[figure not shown]
Table 7. Transformation of SF-36 items to a Scale from 0 to 100

Question	Self-perceived health
----------	-----------------------

	0 (Poor)	100 (Better)
1, 2, 6, 8, 9a, 9d, 9e, 9h, 11b, 11d	5	1
3a to 3j	1	3
4a to 4d, 5a to 5c, 9b, 9c, 9f, 9g, 9i, 10, 11a, 11c	1	5
7	6	1
Programming note: Once transformed – the items should each span the range 0 to 100.		

For each of the 8 dimensions, if less than 50% of the items which constitute that dimension are missing, the dimension score will be calculated by the mean of the available non-missing items. The physical health composite summary and mental health composite summary will only be calculated if a score has been calculated for all 4 dimensions that constitute the composite summary.

Figure 3. SF-36 Model

The mean change from baseline at weeks 12, 28, and 52 weeks will be computed for each treatment group for the following endpoints. A paired t-test will be used to assess within treatment effect. Between treatment difference will be assessed using MMRM using baseline subscore as a covariate and treatment group, visit, the interaction of treatment and visit, and stratification factors as fixed effects. The same strategy as that used in MMRM for Hb will be used to choose variance covariance structure. Non-inferiority of roxadustat vs. Epoetin will be tested. The non-inferiority margin is fixed as a difference of 2 points. Mean change in these endpoints at above-mentioned time points will be analyzed and compared between the 2 treatment groups using MMRM using the baseline value as a covariate, treatment group, visit, the interaction of treatment and visit, adjusting for the stratification factors. The same strategy as that used in MMRM for Hb will be used to choose variance covariance structure. Other than below endpoints for exploratory analyses, other QoL variables may be performed.

HRQoL benefit will be assessed using SF-36 vitality and physical functioning subscales

- **Change from Baseline in SF-36 Vitality (VT) Sub-Score**

The change from baseline in SF-36 VT sub-score to the average VT sub-score will be analyzed using MMRM with baseline VT subscore as a covariate and treatment group, visit, the interaction of treatment and visit, and stratification factors as fixed effects. The same strategy as that used in MMRM for Hb will be used to choose variance covariance structure. Data up to visit of Week 52 will be included in the analyses. The estimates for the difference of change from baseline in SF-36 VT for Week 12 to 28 between two treatment groups will be generated from an estimate statement. Non-inferiority of roxadustat vs. Epoetin will be tested.

- **Change from Baseline in SF-36 Physical Functioning (PF) Sub-Score**

Change from baseline in SF-36 PF sub-score to the average PF sub-score of weeks 12 to 28 will be analyzed using MMRM model with baseline PF subscore as a covariate, treatment group, visit, the interaction of treatment and visit, and stratification factors as fixed effects. The same strategy as that used in MMRM for Hb will be used to choose variance covariance structure. Data up to visit of Week 52 will be included in the analyses. The estimates for the difference of change from baseline in SF-36 PF for Week 12 to 28 between the two treatment groups will be generated from an estimate statement.

- Vitality Sub-score of SF-36: In subjects with baseline vitality sub-score below 50.
- Physical Functioning Sub-scores of SF-36:
 - In FAS subjects with baseline physical Functioning scores below 40.
 - In all FAS subjects.
- Anemia Subscale (“Additional Concerns”) of Functional Assessment of Cancer Therapy-Anemia (FACT-An) Scores:
 - In FAS subjects with baseline subscale scores below 55 (generally associated with fatigue).
 - In all FAS subjects.
- Total FACT-An Scores:
 - In FAS subjects with baseline FACT-An scores below 135
 - In all FAS subjects.
- EQ-5D-5L Scores: In all FAS subjects.

11.3.8 Hepcidin, Iron, and HbA1c

The mean change from baseline in the following endpoints will be analyzed using MMRM model with baseline value as a covariate, treatment group, visit, the interaction of treatment and visit, and stratification factors as factors. The same strategy as that used in MMRM for Hb will be used to choose variance covariance structure

- Change in serum hepcidin at each of the selected time points during which tested, weeks 4, 12, 20, 36, and 52.
- Change in serum ferritin at each of the selected time points it was tested, week 4, 8, 12, 20, 28, 36, 44 and 52, total and sub-grouped by baseline values of <100 ng/mL, 100 to 400 ng/mL, and \geq 400 ng/mL.
- Change in TSAT at each of the selected time points, week 4, 8, 12, 20, 28, 36, 44 and 52, total and sub-grouped by baseline values of < 20%, 20 to 40, and \geq 40%.
- Change in HbA1c level at each of the selected time points, week 12, 24, 36 and 52, in subjects without history of diabetes, in subjects with history of diabetes.

12 SAFETY ANALYSES

The safety analysis will be performed using the Safety Population.

For US regulatory submission, safety analyses will be based on all patients overall and stratified by stable dialysis and newly initiated dialysis,

Safety parameters include adverse events, laboratory parameters, vital signs, ECG parameters, and physical examinations.

The cardiovascular safety assessment of roxadustat will also be based on pooled analysis of composites of adjudicated cardiovascular events pooled across multiple global Phase 3 clinical studies which includes this study, according to the pooled SAPs for meeting regional regulatory requirements.

For each safety parameter, the last assessment made prior to the first dose of study medication will be used as the BL for all analyses of that safety parameter.

12.1 Adverse Events

Adverse events will be coded using the latest MedDRA version. An AE (classified by preferred term) started during the Treatment Period will be considered a treatment-emergent adverse event (TEAE) if it was not present prior to the first dose of study medication, or it was present prior to the first dose of study medication but increased in severity during the Treatment Period up to 7 days after last dose of study drug or until the administration of another anemia drug (other than the randomized treatment). An AE that occurs more than 7 days after study medication or after the administration of another anemia drug (other than the randomized treatment) will not be counted as a TEAE.

The number and percentage of subjects reporting TEAEs in each treatment group will be tabulated by system organ class and preferred term; by system organ class, preferred term, and severity; and by system organ class, preferred term, and relationship to study medication. If more than one event occurs with the same preferred term for the same subject, the subject will be counted only once for that preferred term using the most severe and most related occurrence for the summarization by severity and by relationship to the study medication. The distribution of TEAEs by severity and relationship to study medication will be summarized by treatment group.

The incidence of common ($\geq 5\%$ of subjects in any treatment group) TEAEs, treatment-emergent serious AEs (TESAE), and AEs leading to discontinuation of study medication will be summarized by SOC, preferred term and treatment group, sorted in decreasing frequency for the test treatment. In addition, the incidence of death and fatal SAEs (i.e., events that caused death) will be summarized separately by treatment group, SOC and preferred term. Treatment emergent adverse events of interest will also be reported in terms of incidence rate per Patient Exposure Year (PEY).

Discontinuation of study medication due to worsening anemia based on hemoglobin value (lack of efficacy) will not be counted under AEs leading to discontinuation.

Listings will be presented of subjects with serious adverse events (SAEs), subjects with adverse events leading to discontinuation, and subjects who died.

Temporal profile of TEAEs of special interest may also be plotted by treatment group showing the subjects in the y-axis and time to these TEAEs in the x-axis (Appendix 8).

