## **8.3 Procedures for Eliciting, Recording, and Reporting Adverse Events**

### **8.3.1 Adverse Event Reporting Period**

The study period during which all AEs and SAEs must be reported begins after informed consent is obtained and ends at End of Study / 4-Week post ET/EOT Visit, except for pregnancy reporting (Section 8.3.6).

Adverse events will be followed until resolved, stable, or until the subject’s last study visit or lost to follow-up. If an AE is not resolved or stabilized at the subject’s last visit, it is up to the discretion of the investigator and study medical monitor to determine if further monitoring of the event is warranted.

Adverse events collected prior to dosing of study drug will be considered “nontreatment emergent” while those reported after the first dose of study drug and up to 28 days after the ET/EOT Visit will be considered “treatment emergent” and be assessed for relationship to study drug. If an AE starts on Day 1, the investigator must assess as to whether the AE started prior to or after the administration of study medication and record accordingly.

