#### **9.4.4.1 Adverse Events**

Adverse events will be coded using the Medical Dictionary for Regulatory Activities (MedDRA).

An AE (classified by preferred term) occurring during the Treatment Period will be considered a treatment emergent AEs (TEAE) if it was not present prior to the first dose of study medication, or if it was present prior to the first dose of study medication but increased in severity during the Treatment Period. An AE that occurs more than 28 days after the ET/EOT Visit date will not be counted as a TEAE.

The number and percentage of subjects reporting TEAEs in each treatment group will be tabulated by system organ class and preferred term; by system organ class, preferred term, and severity; and by system organ class and preferred term. If more than one event occurs with the same preferred term for the same subject, the subject will be counted only once for that preferred term using the most severe and most related occurrence for the summarization by severity and by relationship to the study medication.

The overall distribution of TEAEs by severity and relationship to study medication will be summarized by treatment group.

The proportion of subjects with TESAE, fatal SAEs (ie, events that caused death), and AEs leading to permanent discontinuation of study medication will be summarized by System Organ Class (SOC), preferred term and treatment group

Treatment emergent adverse events of interest will also be reported in terms of incidence rate per Patient Exposure Year (PEY).

Listings will be presented of subjects with SAEs, subjects with AEs leading to discontinuation, and subjects who died.

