## 9.6 Statistical Analysis Plan

The Statistical Analysis Plan (SAP) will provide details of the data analyses. As an open-label study the SAP will be finalized prior to accumulation of a substantial amount of data to ensure lack of bias. Any significant changes to the analyses described in this protocol will be highlighted in the SAP and detailed in the Clinical Study Report.

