11 EFFICACY ANALYSES

Efficacy will be conducted on the ITT and FAS for US (FDA) submission. Efficacy analysis of non-inferiority on the PPS population and superiority on FAS population will be used for EU regulatory submission.

The **Efficacy Emergent Period** is defined as the evaluation period from the Analysis date of first dose intake up to 7 days after the Last Dose of study drug or EOT Visit, whichever occurs first. This period will be used as reference period for the time to event analyses related to efficacy endpoints, unless specified otherwise.

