11.3.2 Hospitalizations

Hospitalizations are collected in the Hospitalization Records Form of the eCRF. For each subject, an entry will be recorded for each hospitalization. The days of hospitalization will be calculated as the sum of all hospitalizations durations in days (Date of discharge – Date of Admission + 1). In case of missing dates, the hospitalization duration will be assumed to be 5 days.

Only hospitalizations with admission dates that occur during the Treatment Period and up to 7 days after the last study medication date will be taken into account.

The following hospitalization-related data will be analyzed and compared between the 2 treatment groups:

- Time to first hospitalization (% of subjects) up to Week 52, 7 days after last dose.
- Time to first hospitalization or skilled nursing facility (% of subjects) up to Week 52, 7 days after last dose.
- Number of days of hospitalizations
- Number of days of medical-facility
- Number of days of hospitalizations per patient-exposure year (PEY).
- Number of days in hospital or skilled nursing facility per patient-year exposure (PEY).
- Number of days of medical-facility (hospital, skilled nursing facility, emergency room, or overnight observation) per subject-exposure year (PEY).
- Number of days on treatment out of hospital and skilled nursing facility up to Week 52, 7 days after Last Dose.

Note: Sensitivity analysis may be performed by excluding elective procedures using only hospitalization due to AE

The time to hospitalization event will be compared between the two treatment groups using cox model including baseline stratification factors. The proportion of subjects hospitalized will be compared between the 2 treatment groups using logistic regression model and stratified by the baseline stratification factors. The mean number of days of hospitalization will be analyzed and compared between the 2 treatment groups using the Mantel-Haenszel mean score test adjusting for stratification factors.

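### The SAP's treatment-emergent window (7 days after last dose, or another anemia drug) departs from the protocol's 28 days after ET/EOT without saying so, and its drug cut-off can work differently in the two arms

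*SAP*

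**What the plan says.** **Protocol.** Section 8.3.1 treats as treatment-emergent "those reported after the first dose of study drug and up to 28 days after the ET/EOT Visit". Section 9.4.4.1 gives the same limit: "An AE that occurs more than 28 days after the ET/EOT Visit date will not be counted as a TEAE". Neither section ends the window when another drug is given. Section 9.6 adds: "Any significant changes to the analyses described in this protocol will be highlighted in the SAP".

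**SAP.** Section 12.1 ends the window 7 days after the last dose or when another anemia drug is given. It then excludes "An AE that occurs more than 7 days after study medication or after the administration of another anemia drug (other than the randomized treatment"). The SAP does not define the term for the other drug, and does not say whether counting restarts when study drug resumes. Section 1 presents the SAP as an elaboration of protocol Amendment 2, and no numbered section lists changes from the protocol.

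**Related SAP rules.**
- Section 9.1 runs patient-exposure-years (PEY) from first to last dose, and Section 12.1 uses PEY as the denominator for rates of TEAEs of interest.
- Section 11 defines an efficacy period ending 7 days after the last dose or at the EOT visit, whichever is first: "This period will be used as reference period for the time to event analyses related to efficacy endpoints", unless otherwise specified.
- Section 11.3.2 has a 7-day tail for hospitalizations ("Only hospitalizations with admission dates that occur during the Treatment Period and up to 7 days after the last study medication date"), and Section 11.3.3 has one for missed dialyses. None of these three windows has a drug rule.
- The TEAE flag defines events in two additional efficacy endpoints. Section 11.3.5: "Time to a TEAE of hypertension will be analyzed using the Cox Proportional Hazards model". Section 11.3.6: "Time to a TEAE of vascular access thrombosis will be analyzed using the Cox Proportional Hazards model".

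**The concern.** There are two separate problems.

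The first is an undeclared change of definition. AEs are collected to 4 weeks after ET/EOT, but the SAP tables would drop most of the post-treatment events that the protocol calls treatment-emergent.

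The second, and more serious, is the drug cut-off. Taken literally, and if the window does not reopen, one ESA dose removes all later on-treatment events for that subject from the TEAE and TESAE tables. Protocol 4.6.3.2 lets roxadustat continue after an inadvertent or hospital ESA dose and has it resumed after ESA rescue, so real on-treatment time is at stake. The arms are not treated alike. For a roxadustat subject every ESA is another anemia drug. For an epoetin subject, SAP 11.3.3.2 records extra epoetin alfa as a study-drug dose change, so among ESAs only a different analogue triggers the cut. The protocol's rationale for Amendment 2 says ESA use during hospitalization is common in roxadustat subjects. The trigger may therefore fall on subjects who have just been ill.

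Events would be cut while PEY and the default time-to-event period are not. If triggers are more frequent on roxadustat, this lowers its TEAE and TESAE counts and its per-PEY rates. It also lowers the hazard ratios for TEAEs of hypertension and access thrombosis, unless subjects are censored at the trigger. Safety is part of the primary objective, and Protocol 2.2 names hypertension and thrombosis among the ESA risks.

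**Working it through.** The plan gives no figure to reproduce, and no ESA-use rate. The numbers below illustrate size and are not estimates. pR and pE are the shares of roxadustat and epoetin subjects who trigger the cut. Exposure is 52 weeks (364 days), the event rate is constant and the true ratio is 1.

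**Post-treatment tail.** If ET/EOT falls on the last-dose date, the protocol counts 28 days and the SAP 7, so 28 − 7 = 21 days of collected events drop out. If ET/EOT is 7 days after the last dose (assumption), 35 − 7 = 28 days drop out.

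**(A) Literal reading, window never reopens, trigger time uniform over exposure, PEY not cut.** Events kept per arm = 1 − p/2. Apparent ratio = (1 − pR/2)/(1 − pE/2).

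| pR | pE = 0 | pE = 5% |
|---|---|---|
| 5% | 0.975 | 0.975/0.975 = 1.000 |
| 10% | 0.950 | 0.950/0.975 = 0.974 |
| 20% | 0.900 | 0.900/0.975 = 0.923 |
| 30% | 0.850 | 0.850/0.975 = 0.872 |

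With pR = 10% and pE = 20%, the ratio reverses: 0.950/0.900 = 1.056.

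Timing matters. If all triggers fall at week t, the fraction kept is 1 − p(1 − t/52). For p = 10% this is 0.919 at week 10, 0.950 at week 26 and 0.977 at week 40.

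**Cox models under (A).** Simulation with exponential events, true hazard ratio 1, 40,000 subjects per arm, 8 runs and pE = 0:

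| pR | Incidence | Risk time not cut | Censored at trigger |
|---|---|---|---|
| 10% | 10% | 0.946 | 0.998 |
| 10% | 20% | 0.952 | 0.993 |
| 20% | 10% | 0.906 | 1.001 |
| 20% | 20% | 0.900 | 0.995 |

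The bias comes from cutting events without cutting time at risk. Censoring at the trigger removes nearly all of it in this setting, where triggers are unrelated to event risk.

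**(B) Window reopens when study drug resumes after one ESA rescue cycle at the 4-week limit.** Protocol 4.6.3.2 has study treatment resume 2 days (epoetin) to 14 days (Mircera) after stopping, so 28 + 2 = 30 to 28 + 14 = 42 days are lost. Ratio = 1 − pR × d/364 with pE = 0:
- pR = 10%: 0.992 to 0.988
- pR = 20%: 0.984 to 0.977

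**(C) Drug rule applies only to the post-treatment tail.** No on-treatment time is lost. Protocol 4.1.3 allows an ESA from 3 days after the last roxadustat dose. A roxadustat tail can then be 3 days against 7 on epoetin, if epoetin alfa continued after EOT counts as the randomized treatment. The gap as a share of counted time for an affected subject is 4/(exposure days + 7):
- 52 weeks: 4/371 = 1.1%
- 8 weeks: 4/63 = 6.3%
- 4 weeks: 4/35 = 11.4%

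**The case against.** **The tail-only reading is plausible.** The first sentence in SAP 12.1 can be read as giving two alternative ends to the post-treatment window, with the second as its mirror image. Scenario C then applies and little is lost at 52 weeks. But the second sentence is not limited to the tail, and a programmer following it would drop on-treatment events.

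**The larger ratios stack assumptions.** They need the literal reading, no reopening, and 10% to 30% of roxadustat subjects triggering. ESA rescue has four criteria and is limited to one cycle, and it may end before 4 weeks. This stands as a limit on size. Inadvertent and hospital use, however, fall outside the rescue limits, and their frequency is not given.

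**The hazard-ratio effect depends on censoring.** This is correct. SAP 11.3.5 and 11.3.6 specify no censoring at the trigger, so the default period in SAP 11 applies, and that period is not cut.

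**A 7-day on-treatment window is defensible.** Protocol 2.4.1 gives a half-life of 15 to 19 hours in dialysis subjects, so 168 hours is about 9 to 11 half-lives, and other SAP windows use the same tail. This stands for the tail, but not for the drug rule, which those windows lack.

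**Other analyses do not use the flag.** Blood-pressure exacerbation and mean arterial pressure are in the fixed sequence, access thrombosis is also adjudicated, and the two Cox endpoints lie outside the multiplicity procedure. These points limit the consequence but leave the TEAE and TESAE tables exposed.

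**The SAP front matter was not available**, so a note there cannot be excluded.

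**Conclusion.** The concern holds and should be fixed. The conflict between the protocol and SAP windows is certain from the text, and no numbered SAP section highlights it. As written, the drug cut-off is undefined, silent on reopening, and open to different operation by arm. The per-PEY rates, and by default the two Cox models, would set cut events against uncut time.

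The size and direction of any bias are unknown, because they depend on ESA use in each arm. The range runs from no on-treatment loss (tail-only), through 1% to 2% with reopening, to 5% to 10% on the literal reading with 10% to 20% of roxadustat subjects triggering and none on epoetin. More triggers on epoetin would reverse it. SAE listings and pooled adjudicated cardiovascular events do not rest on this flag. Deaths and fatal SAEs are summarized separately, although SAP 12.1 states no window for them.

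**What to change.** Reconcile SAP 12.1 with Protocol 8.3.1 and 9.4.4.1:

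1. Report the protocol-defined TEAE analysis (to 28 days after ET/EOT, no drug cut) beside the 7-day on-treatment analysis. State which is main and that the 7-day version departs from the protocol.
2. Do not end flagging at another anemia drug while the subject continues or resumes study drug.
3. Wherever a drug-truncated version is kept, define the drugs that count (for example, ESAs but not iron) and say whether the window reopens.
4. Compute person-time for AE rates, and time at risk in the SAP 11.3.5 and 11.3.6 TEAE Cox models, over the same window as the events.
5. Report per arm how many subjects trigger the drug cut.

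The cost is SAP wording, one extra TEAE flag, one person-time variable per window and one extra set of TEAE tables. No new data are needed.

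The 28-day window has a drawback: it can assign ESA time to roxadustat. If ET/EOT is on the last-dose date and an ESA starts on day 3, up to 28 − 3 = 25 days are affected. As a share of counted time this is 25/392 = 6.4% after 52 weeks, 25/84 = 30% after 8 weeks and 25/56 = 45% after 4 weeks, which is why both windows should be shown. Person-time must also be extended. A 28-day tail over PEY ending at the last dose would overstate rates in both arms by 28/364 = 7.7% at 52 weeks and 28/56 = 50% at 8 weeks. For a 7-day tail the figures are 7/364 = 1.9% and 7/56 = 12.5%.
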